6.3 Procedures for handling subjects with premature study discontinuation

In the absence of a medical contraindication or significant protocol violation, every effort will be made by the Investigator to keep the subject in the study. If a subject has to be withdrawn, all efforts will be made to complete and report the trial observations as thoroughly as possible. If a subject needs to be withdrawn, all efforts shall be made to follow safety of the subject as per protocol.

Subjects who withdraw or are withdrawn from the study prior to treatment application will be replaced. No follow-up of these subjects will be performed and no data will be analyzed. Subjects withdrawing or withdrawn after treatment application will not be replaced if study recruitment has already been terminated, and their data will be analyzed under the intention-to-treat (ITT) principle.

When a subject withdraws from the study before the planned end of the study period, all investigations scheduled for the end-of-study visit should be performed if the subject agrees. End-of-study evaluation will be completed at the time of the subject's withdrawal, with an explanation of the reason for this entered onto the respective "end-of-study" section of the CRF as follows:

- Adverse event (specify);
- Death;
- Protocol violation (specify);
- Medical condition (specify);
- Consent withdrawal, not due to AE;
- Other (specify).

6.4 Breaking the randomization code

The treatment codes will be held separately from the clinical investigators in charge of assessing the occurrence of adverse events and breaking the blind will be done only at study end.

Breaking the blind for a single subject will be considered when knowledge of the treatment assignment is deemed essential by the subject's physician for the subject's care.

Additionally, in the event of a SUSAR or a holding rule activation, the blind may be broken for the purposes of reporting to Swissmedic and/or determination of trial feasibility, respectively. Any intentional or unintentional breaking of the blind will be reported and explained at the end of the trial, irrespective of the reason for its occurrence. The procedure and timing for revealing the treatment assignments will be documented as well. All calls resulting in an unblinding event will be recorded and reported by the IWRS to the Medical Monitor and the Sponsor.

7 SAFETY ASSESSMENT

Safety will be assessed by the frequency, incidence, severity and nature of adverse events and serious adverse events arising during the study.

7.1 Adverse events

An AE is any untoward medical occurrence in a subject that may occur during or after administration of an Investigational Medicinal Product (IMP) and does not necessarily have a causal relationship with the intervention. An AE can therefore be any unfavorable and unintended sign (including an abnormal laboratory finding), symptom or disease temporally associated with the study intervention, whether or not considered related to the study intervention.

Each AE will be graded according to the tables for AE severity below (7.8 Assessment of severity). The following guidelines will be used to determine whether or not an AE is recorded in the study database:

- Solicited AE (*i.e.*, reactogenicity parameters) will be recorded on diary cards in the 7 days and recorded in the CRF in the 7 days following treatment;
- Unsolicited AE of all severities will be recorded on diary cards in the 7 days and recorded in the CRF in the 28 days following treatment;
- SAE (as defined in 7.3 Serious adverse events) will be recorded in the CRF in the 28 days following treatment.

7.2 Adverse reactions

An adverse reaction (AR) is any untoward or unintended response to an IMP. This means that a causal relationship between the IMP and an AE is at least a reasonable possibility, i.e., the relationship cannot be ruled out. All cases judged by the reporting Investigator as having a reasonable suspected causal relationship to an IMP (i.e. possibly, probably or definitely related to an IMP) will qualify as AR.

7.3 Serious adverse events

A SAE is an AE that results in any of the following outcomes, whether or not considered related to the study intervention:

- Death;
- Life-threatening event (i.e., the subject was, in the view of the Investigator, at immediate risk of death from the event that occurred). This does not include an AE that, if it occurred in a more severe form, might have caused death;
- Persistent or significant disability or incapacity (i.e., substantial disruption of one's ability to carry out normal life functions);
- Hospitalization, regardless of length of stay, even if it is a precautionary measure for continued observation. Hospitalization (including inpatient or outpatient hospitalization for an elective procedure) for a pre-existing condition that has not worsened unexpectedly does not constitute a SAE;
- An important medical event (that may not cause death, be life-threatening, or require hospitalization) that may, based upon appropriate medical judgment, jeopardize the subject and/or require medical or surgical intervention to prevent one of the outcomes listed above. Examples of such medical events include allergic reaction requiring intensive care in an emergency room or clinic, blood dyscrasias, or convulsions that do not result in inpatient hospitalization;
- Congenital anomaly or birth defect.

7.4 Serious adverse drug reaction (SADR)

An event that is expected or unexpected and is both serious and, in the opinion of the reporting investigator or Sponsors, believed to be possibly, probably or definitely due to an IMP or any other study treatments, based on the information provided, is considered a serious adverse drug reaction (SADR or SAR).

7.5 Suspected unexpected serious adverse reaction (SUSAR)

A SUSAR is an SAE that is unexpected and thought to be possibly, probably or definitely related to an IMP. No category of SAE has been defined as 'expected.'

7.6 Causality assessment

For every AE, an assessment of the relationship of the event to the administration of the vaccine will be undertaken. An intervention-related AE refers to an AE for which there is a probable or definite relationship to administration of a vaccine.

The degree of certainty with which an AE can be attributed to administration of the study vaccine(s) (or alternative causes, e.g. natural history of the underlying diseases, concomitant therapy, etc.) will be determined by how well the event can be understood in terms of one or more of the following:

- related** suspicion that there is a relationship between vaccine and AE (without determining the extent of probability); there is a reasonable possibility that the vaccine contributed to the AE
- unrelated** there is no suspicion that there is a relationship between vaccine and AE, there are other more likely causes and administration of the study vaccine is not suspected to have contributed to the AE

The causality assessment will be made on the basis of the available information at the reporting time point and apply to both AEs and SAEs. Assessment of causality can change according to follow-up information.

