8.2 Safety analysis

The safety analysis will include all randomized subjects who have received a dose of study vaccine. The overall percentage of subjects with at least one spontaneously reported adverse event, with date of onset up to 28 days after vaccination will be tabulated with exact 95% confidence intervals, by type of adverse event; by severity; and by causality. They will be displayed by vaccine group as both frequencies and percentages on the ITT data set.

All reported adverse events that start post-vaccination will be tabulated. If a given disease is already reported as ongoing at the first visit on the medical history pages, it will be counted and tabulated as a vaccine emergent adverse event only if it worsens after the immunization with the study vaccine. Serious adverse events and discontinuation due to adverse event(s) will be described in detail by vaccine group.

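### Section 7.6 restricts an intervention-related AE to a probable or definite link, which conflicts with its own related/unrelated scale and with 7.2, 7.4 and 7.5, all of which include possible events

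*Combined protocol and SAP*

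**What the plan says.** All references are to the combined protocol and SAP.

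- **7.6, opening paragraph:** "An intervention-related AE refers to an AE for which there is a probable or definite relationship to administration of a vaccine". Possible events are left out.
- **7.6, scale:** two categories. 'Related' is a "suspicion that there is a relationship between vaccine and AE (without determining the extent of probability"), and the entry adds that "there is a reasonable possibility that the vaccine contributed to the AE". 'Unrelated' requires that "there is no suspicion that there is a relationship between vaccine and AE". The section applies this assessment to AEs and SAEs alike.
- **7.2 (adverse reactions):** the bar is at least a reasonable possibility, and cases judged "possibly, probably or definitely related to an IMP) will qualify as AR".
- **7.4 (SADR):** the same three grades, possible, probable and definite, all count.
- **7.5 (SUSAR):** an unexpected SAE "thought to be possibly, probably or definitely related to an IMP". The section adds that no category of SAE has been defined as expected.
- **7.7.1 and 7.7.2:** every SAE is reported, and its code may be broken if needed. A SUSAR is reported within 24 hours and its code is to be broken.
- **8.2:** AEs are tabulated "by type of adverse event; by severity; and by causality", with no statement of which causality rule defines a related event.

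**The concern.** Causality is the item in the safety data that depends most on the assessor's judgement, so its threshold has to be written once and the same way everywhere. Here an investigator who reads 7.6 from the top meets the stricter threshold first and the broader scale second. An event judged possibly related falls on opposite sides of the line depending on which of the two is followed.

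Two outputs depend on that call. One is the related-AE count by group in 8.2, which serves the first-listed secondary objective, the safety comparison of two doses with one. The other is the SUSAR classification. Since 7.5 treats no SAE as expected, every SAE judged related is a SUSAR, and causality is the only remaining gate to the expedited report and the code break.

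**Working it through.** No figure in the plan can be reproduced here, because the point concerns definitions. The check is to take one event judged possibly related and classify it under each rule.

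| Rule | Threshold | Possibly related event |
|---|---|---|
| 7.2 adverse reaction | possible, probable or definite | counts |
| 7.4 SADR | possible, probable or definite | counts, if serious |
| 7.5 SUSAR | possible, probable or definite | counts, if serious and unexpected |
| 7.6 two-category scale | reasonable possibility | related |
| 7.6 opening paragraph | probable or definite | not intervention-related |

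**Step 1. Which rule is out of line.** Four of the five agree. Section 7.2 ties the two vocabularies together: it sets the bar at a reasonable possibility and spells that out as possible, probable or definite. The 7.6 scale uses the same bar. Only the opening paragraph of 7.6 differs.

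**Step 2. Whether the stricter sentence can be applied to recorded data.** It cannot. The scale does not grade probability, so a record of 'related' does not separate possible from probable or definite. The sentence can act only when the assessor makes the call, and the record would not show that it had done so.

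**Step 3. Effect on the 8.2 table.** If an assessor lets the stricter sentence govern, a possibly related event is entered as unrelated and leaves the related count. With 50 participants per group, moving one participant changes that group's percentage with a related AE by 1/50 = 2 percentage points, provided the participant has no other related AE.

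**Step 4. Effect on an SAE.** Compare the two routes for the same event, reading 'non-lethal' in 7.7.1 as neither fatal nor life-threatening.

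| SAE | Classified as SUSAR (7.7.2) | Recorded as unrelated (7.7.1) |
|---|---|---|
| Neither fatal nor life-threatening | report within 24 hours; code to be broken | report within 7 calendar days; code broken only if deemed necessary |
| Fatal or life-threatening | report within 24 hours; code to be broken | report within 24 hours; code broken only if deemed necessary |

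The permitted reporting time lengthens by up to 7 − 1 = 6 days in the first row and does not change in the second. The code break ceases to be required in both. In no case does the SAE go unreported.

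**The case against.** The strongest reply is that the stricter sentence does no work. Section 8.2 never uses the term it defines, and no tabulation, reporting or withdrawal rule refers to it. The scale that assessors are asked to use already agrees with 7.2, 7.4 and 7.5, and 'unrelated' on that scale requires the absence of any suspicion, which a possible case does not meet. The safeguards are also broad: 7.7 records all AEs within 28 days whatever their attribution, 7.7.1 reports every SAE without a causality condition, and 8.2 tabulates by type and severity and describes SAEs by group. The CRF is said in 11.3 to accompany the protocol but is not among the documents, so the categories actually captured cannot be checked.

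Most of this stands, and it rules out several stronger readings that a reader might infer:

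- **That the 8.2 table and the SUSAR trigger necessarily rest on different rules.** Section 8.2 names no rule. If it uses the recorded related/unrelated category as the scale defines it, the two agree in substance.
- **That the two-category scale causes the divergence.** The scale agrees with the other sections. It simply cannot supply the grading that the sentence above it needs.
- **That an analyst could drop possible events afterwards.** Data recorded on the scale would not allow it.
- **That possibly related SAEs would escape reporting.** They would still be reported under 7.7.1.

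The reply does not remove the contradiction. The sentence is current text in the section that governs causality, it stands ahead of the scale, and nothing says the scale overrides it. An assessor who follows it is following the protocol.

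**Conclusion.** The point holds as an inconsistency that should be corrected. The opening paragraph of 7.6 conflicts with the scale in the same section and with 7.2, 7.4 and 7.5. That much is certain from the text.

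The consequence is conditional: it arises only if an assessor lets the sentence govern the related/unrelated call. In that case the related count in 8.2 is too low and, for an SAE that is neither fatal nor life-threatening, the 24-hour report and the required code break are lost. If assessors use the scale as written, the effect is nil.

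The documents give neither the share of AEs that would be judged only possibly related nor the proportion of assessors who would apply the sentence, so no percentage reduction can be stated. The 2 points per participant in the working is a unit of measurement and says nothing about how often a reclassification would occur. The safety analysis is descriptive, and the primary endpoint and sample size are untouched.

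**What to change.** 1. Delete the sentence in 7.6 that limits an intervention-related AE to probable or definite.
2. State once, and apply in 7.2, 7.4, 7.5 and 7.6, that possible, probable and definite all map to 'related', meaning a reasonable possibility that the vaccine contributed.
3. State in 8.2 that the causality table uses the recorded related/unrelated category.
4. Check that the CRF carries the same two categories, or, if it is graded, that it uses the mapping in item 2.

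The cost is one deletion, one mapping statement and one clause in 8.2. If the CRF already records related/unrelated, no new data are needed. The related-AE count may come out higher than it would under the deleted sentence. The change is best made before assessors have classified events, since a call made under the stricter sentence cannot be identified from the two-category record.

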7.7 Reporting procedures for all adverse events

All AEs and SAEs occurring within the 28 days following treatment and observed by the Investigator or reported by the volunteer, whether or not attributed to study intervention, will be recorded in the CRF. All AEs that result in a volunteer's withdrawal from the study will be followed up until a satisfactory resolution occurs, or until a non-study related causality is assigned (if the volunteer consents to this).

7.7.1 Reporting procedures for SAE

Following the occurrence of any SAE, the trial subject's randomization code may be broken if deemed necessary (see 6.4 Breaking the randomization code). The PI/Sponsor shall report the SAE to the CCER, BioNet-Asia Pharmacovigilance and Swissmedic, as soon as learning that the event meets the definition of a SAE and no later than 24h for fatal or life-threatening SAE and 7 calendar days for non-lethal SAE. The minimum information included in the initial SAE report will contain: subject's number, date of birth, description of the event, study vaccine (date of vaccination), reporter information and causality assessment.

Important follow-up information shall be reported when available. If relevant information is missing at the time of the initial SAE report, the reporter shall provide it in follow-up SAE report(s). A follow-up report shall contain new, updated or corrected information. The follow-up report shall describe whether the event has resolved or continues, if and how it was treated including documentation of all supportive actions taken, and whether the blind was broken or not.

7.7.2 Reporting procedures for SUSAR

Following the occurrence of a SUSAR, the trial subject's randomization code shall be broken (see 6.4 Breaking the randomization code) and the PI shall report the event to the CCER, BioNet-Asia Pharmacovigilance and Swissmedic within 24h of learning that the event meets the definition of a SUSAR.

[figure not shown]

Figure 5. Workflow for reporting of serious adverse events and SUSAR

7.8 Assessment of severity

The severity of clinical and laboratory AE will be assessed according to the scales in Tables 5-7.

Table 5. Toxicity grading scale for local adverse events

Toxicity grading scale for local adverse events						
Local Reaction	Grade 0	Grade 1a [£] Mild	Grade 1b [†] Mild	Grade 2 Moderate	Grade 3 Severe	Grade 4 Potentially life-threatening
Redness/Erythema*	None	<25 mm	25-50 mm	51-100 mm	>100 mm	Necrosis or exfoliative dermatitis
Swelling/Induration**	None	<25 mm	25-50 mm and does not interfere with activity	>50 mm or interferes with activity	Prevents daily activity	Necrosis
Pain	None	-	Does not interfere with activity	Interferes with activity	Prevents daily activity	Emergency room visit or hospitalization

[£]Grade 1a = when localized under the patch; [†]Grade 1b = mild but extending beyond the patch

*In addition to grading the measured local reaction at the greatest single diameter, the measurement should be recorded as a continuous variable.

**Induration/swelling should be evaluated and graded using the functional scale as well as the actual measurement.

Adapted from the FDA's 2007 voluntary guidance:

<http://www.fda.gov/downloads/BiologicsBloodVaccines/GuidanceComplianceRegulatoryInformation/Guidances/Vaccines/ucm091977.pdf>.

Table 6. Toxicity grading scale for Vital signs

Vital signs					
Observation	Grade 1	Grade 2	Grade 3	Grade 4	Grade 5
Fever (axillary)	38.0° - 39.0°C	>39.0°C - 40.0°C	>40.0°C for ≤24 hours	>40.0°C for ≥24 hours	Death
Tachycardia (bpm)*	Asymptomatic, intervention not indicated	Symptomatic, non-urgent medical intervention indicated	Urgent medical intervention indicated	Life-threatening consequences, urgent intervention indicated	Death
Bradycardia (bpm)**	Asymptomatic, intervention not indicated	Symptomatic, medical intervention indicated	Severe, medically significant, urgent medical intervention indicated	Life-threatening consequences, urgent intervention indicated	Death
Hypertension**	Prehypertension (systolic BP 120 - 139 mm Hg or diastolic BP 80 - 89 mm Hg)	Stage 1 hypertension (systolic BP 140 - 159 mm Hg or diastolic BP 90 - 99 mm Hg); medical intervention indicated; recurrent or persistent (≥24h); symptomatic increase by >20 mm Hg (diastolic) or to >140/90 mm Hg if previously WNL; monotherapy indicated	Stage 2 hypertension (systolic BP ≥160 mm Hg or diastolic BP ≥100 mm Hg); medical intervention indicated; more than one drug or more intensive therapy than previously used indicated	Life-threatening consequences (e.g., malignant hypertension, transient or permanent neurologic deficit, hypertensive crisis); urgent intervention indicated	Death
Hypotension	Asymptomatic, intervention not indicated	Non-urgent medical intervention indicated	Medical intervention or hospitalization indicated	Life-threatening and urgent intervention indicated	Death
Definitions					
Fever	A disorder characterized by elevation of the body's temperature above the upper limit of normal.				
Tachycardia	A disorder characterized by a dysrhythmia with a heart rate greater than 100 beats per minute.				
Bradycardia	A disorder characterized by a dysrhythmia with a heart rate less than 60 beats per minute.				
Hypertension	A disorder characterized by a pathological increase in blood pressure; a repeatedly elevation in the blood pressure exceeding 140 over 90 mm Hg.				
Hypotension	A disorder characterized by a blood pressure that is below the normal expected for an individual in a given environment.				

*Taken after ≥10 minutes at rest; **when resting heart rate is between 60 - 100 beats per minute. Use clinical judgment when characterizing bradycardia among some healthy subjects, for example, conditioned athletes.

From CTCAE v4 (http://evs.nci.nih.gov/ftp1/CTCAE/CTCAE_4.03_2010-06-14_QuickReference_5x7.pdf)

Table 7. Toxicity grading scale for systemic AEs excluding the vital signs listed above

Toxicity grading scale for systemic adverse events				
Systemic sign/symptom	Grade 1 Mild	Grade 2 Moderate	Grade 3 Severe	Grade 4 Potentially life-threatening
Headache	No interference with activity	Some interference with activity	Significant; prevents daily activity	Medical consultation and/or hospitalization
Fatigue	No interference with activity	Some interference with activity	Significant; prevents daily activity	Medical consultation or hospitalization
Myalgia	No interference with activity	Some interference with activity	Significant; prevents daily activity	Medical consultation and/or hospitalization
Arthralgia	No interference with activity	Some interference with activity	Significant; prevents daily activity	Medical consultation and/or hospitalization
Chills	No interference with activity	Some interference with activity	Significant; prevents daily activity	Medical consultation and/or hospitalization
Sweats	No interference with activity	Some interference with activity	Significant; prevents daily activity	Medical consultation and/or hospitalization
Subjective Fever	No interference with activity	Some interference with activity	Significant; prevents daily activity	Medical consultation and/or hospitalization
Nausea	No interference with activity	Some interference with activity not requiring medical intervention	Prevents daily activity and requires medical intervention	Medical consultation and/or hospitalization
Vomiting	No interference with activity	Some interference with activity not requiring medical intervention	Prevents daily activity and requires medical intervention	Medical consultation and/or hospitalization
Abdominal Pain	No interference with activity	Some interference with activity not requiring medical intervention	Prevents daily activity and requires medical intervention	Medical consultation and/or hospitalization
Diarrhea	No interference with activity	Some interference with activity not requiring medical intervention	Prevents daily activity and requires medical intervention	Medical consultation and/or hospitalization
Other systemic symptoms	No interference with activity	Some interference with activity	Prevents daily activity	Medical consultation and/or hospitalization

From the FDA's 2007 voluntary guidance:
<http://www.fda.gov/downloads/BiologicsBloodVaccines/GuidanceComplianceRegulatoryInformation/Guidances/Vaccines/ucm091977.pdf>

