5.1.2 Phone contact (Day 7 +/-1)

Study participants will be contacted by phone at Day 7 to confirm that adverse reactions have subsided. Should this not be the case, an unscheduled visit will be considered appropriate.

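### Table 7 lets a medical consultation alone meet Grade 4, at odds with Tables 5 and 6 and overlapping its own lower grades, so Grade 4 counts can mix care-seeking with severity

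*Combined protocol and SAP*

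**What the plan says.** Section 7.1 makes the scales binding: "Each AE will be graded according to the tables for AE severity below". Section 7.8 supplies three of them.

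- **Table 7, systemic events.** The last column is "Grade 4 Potentially life-threatening". The entry for fatigue is "Medical consultation or hospitalization"; for the other 11 rows it is "Medical consultation and/or hospitalization". Those rows are headache, myalgia, arthralgia, chills, sweats, subjective fever, nausea, vomiting, abdominal pain, diarrhea and a catch-all for other systemic symptoms. Grades 1 and 2 depend mainly on interference with activity. For the four gastrointestinal rows, Grade 3 is "Prevents daily activity and requires medical intervention".
- **Table 5, local events.** Grade 4 pain is "Emergency room visit or hospitalization".
- **Table 6, vital signs.** Tachycardia and hypotension that call for non-urgent intervention are Grade 2. For the heart-rate and blood-pressure rows, Grade 4 needs a life-threatening state or consequence.

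Section 8.2 tabulates spontaneously reported events up to 28 days after vaccination, with exact 95% confidence intervals, "by type of adverse event; by severity; and by causality". For solicited reactions, the synopsis says only that they are described by treatment group. On persisting reactions at the Day 7 call, section 5.1.2 says: "Should this not be the case, an unscheduled visit will be considered appropriate".

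**The concern.** A severity scale should rank how ill a participant was. Seeing a doctor depends on that, but also on access, caution and the study's own follow-up. When a consultation is sufficient for the top column of Table 7, a participant who had an ordinary appointment for a minor symptom can be counted beside one who was admitted to hospital.

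Safety of two doses against one is the first-listed secondary objective, and in groups of 50 a few such events would be visible. A reader of the final report would see events labelled potentially life-threatening and could not tell which were severe and which had merely been seen by a doctor. Assessors who meet two matching grades would each have to settle the conflict themselves.

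**Working it through.** The plan states no figure for this point, so the main check sets the criteria side by side.

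**Step 1. Is consultation alone sufficient?** Both the or form (1 row) and the and/or form (11 rows) are met by a consultation without hospitalization. 1 + 11 = 12, which is every row. No row adds a condition on urgency or severity.

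**Step 2. Do the three tables agree?**

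| Scale | Level of care named | Grade |
|---|---|---|
| Table 7, all rows | Consultation alone | 4 |
| Table 5, pain | Emergency room or hospital admission | 4 |
| Table 6, tachycardia and hypotension | Non-urgent intervention | 2 |

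Non-urgent care is Grade 2 in one table and can be Grade 4 in the next. Tables 5 and 7 point to the same guidance document but set different thresholds.

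**Step 3. Are Table 7's grades mutually exclusive?** They are not, in two places.
- Nausea, vomiting, abdominal pain, diarrhea: Grade 3 already includes a need for medical intervention. If that is provided through a consultation, the event meets Grades 3 and 4.
- Any row: a symptom that does not interfere with activity but is seen by a doctor meets Grades 1 and 4.

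No rule says which grade prevails.

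**Step 4. Does this reach a planned output?** By its wording, the severity tabulation in section 8.2 covers spontaneously reported events. Of Table 7's rows, abdominal pain, diarrhea and the catch-all are not on the synopsis list of solicited symptoms as named items, so they feed that tabulation. The other nine rows are solicited through Day 7. They must still be graded under section 7.1 and reach the report through the by-group description.

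**Step 5. Scale, for illustration.** The input is n = 50 per group (section 8.1). One participant is 1/50 = 2 percentage points. The documents give no consultation rate, so p below is an assumption. The expected count is 50p, and the chance of at least one in a group is 1 − (1 − p)^50.

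| Assumed p | Expected per group | Chance of at least one |
|---|---|---|
| 1% | 0.5 | 39% |
| 2% | 1 | 64% |
| 5% | 2.5 | 92% |
| 10% | 5 | 99% |

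Exact (Clopper-Pearson) 95% intervals for the reported Grade 4 percentage are:
- 0/50: 0 to 7.1%
- 1/50: 0.1 to 10.6%
- 3/50: 1.3 to 16.5%
- 5/50: 3.3 to 21.8%

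**The case against.** The case for leaving the table alone is that the column heading signals the intent, blinded assessors will grade sensibly, the same scale applies to both randomized groups, and the analysis is descriptive. Seriousness is defined separately in section 7.3, and neither serious-event nor SUSAR reporting depends on grade. Tables 5 to 7 also grade different reactions, so identical thresholds are not required. Most of this stands and limits the consequence. It does not remove the defect: sensible grading would mean setting aside a written criterion, with no instruction on when to do so.

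A reader might infer four stronger things that the documents do not support.

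- **That the study's own unscheduled visits are Grade 4 events.** Medical consultation is not defined. Counting an on-site visit to the investigator is a natural reading, but it remains a reading. Section 5.2 also allows these visits by phone, and after the Day 7 call a visit is considered rather than automatic.
- **That a mild headache seen at Day 7 must be Grade 4.** It also meets Grade 1, so the text is ambiguous. Headache within 7 days is solicited, and so is outside the section 8.2 severity tabulation as worded.
- **That Grade 3 is emptied for gastrointestinal events.** The grades overlap; it is not shown that every such event would move up.
- **That the comparison of two doses with one would be wrong.** With a common scale and blinded assessment, no differential bias is shown.

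**Conclusion.** The point holds as an inconsistency in the grading scale, with a limited but real effect on reporting. Applied as written, Table 7 can place ordinary care-seeking in a column labelled potentially life-threatening. It disagrees with Tables 5 and 6, and it does not give a unique grade to every event.

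The firm part of the size is 2 percentage points per affected participant. The range of 0.5 to 5 participants per group rests wholly on an assumed consultation rate of 1% to 10%, and also assumes that assessors apply Grade 4 whenever it is met. The effect is confined to how the severity summaries read. The primary neutralizing-antibody comparison is untouched. The correction should be made because it is cheap and the affected output concerns a stated secondary objective.

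**What to change.** Reconcile the Grade 4 criterion in Table 7 with Tables 5 and 6, so that an ordinary consultation, or a scheduled or unscheduled study visit, does not by itself raise the grade. The wording already used for pain in Table 5 is one internally consistent option; the sponsor may choose another, provided that the tables agree. Define medical consultation if the term is kept. Separate Grades 3 and 4 in the four gastrointestinal rows, and state which grade prevails when an event meets more than one. Whether an event was medically attended can be reported as its own item, since section 5.2 already records this at unscheduled visits.

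The cost is an edit to one table and the matching CRF coding. No new visits or data collection are needed. Any events already graded under the present wording should be regraded while assessors remain blinded.
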